14.5 Accuracy Analyses

14.5.1 Two sets of metrics will be calculated:

• Relative (Percent) Difference (RD) for reference result ≥ threshold glucose :

$$RD=\frac{M-C}{C}100\%$$

¹ Draper, N.R., Smith, H., (1998) Applied Regression Analysis, 3rd Ed., John Wiley and Sons, New York

where: M = strip/meter result and C = comparator or reference method result.

Difference (D) for reference result < threshold glucose:

$\boldsymbol{D}=\boldsymbol{M}-\boldsymbol{C}$

14.5.2 Primary objective: The threshold glucose value is 100 mg/dL(5.55 mmol/L). Accuracy will be assessed using the Clinical and Laboratory Standards Institute (CLSI) – Point-of-Care Blood Glucose Testing in Acute and Chronic Care Facilities; Draft Guideline-Third Edition (POCT12 (Draft 4) Vol.0 No.0 Replaces C30-A2 Vol.22 No.17).

i.e., D within $\pm 12 \text{ mg/dL}$ ($\pm 0.67 \text{ mmol/L}$) for comparator result < 100 mg/dL (5.55 mmol/L) and RD within $\pm 12.5\%$ for comparator result $\geq 100 \text{ mg/dL}$ (5.55 mmol/L).

For RD, the percent of results within $\pm 5\%$, $\pm 10\%$, $\pm 12.5\%$, $\pm 15\%$ and $\pm 20\%$ will be computed.

For *D*, the percent less than or equal to $\pm 5 \text{ mg/dL}$ ($\pm 0.28 \text{mmol/L}$), $\pm 10 \text{ mg/dL}$ ($\pm 0.56 \text{ mmol/L}$), $\pm 12.0 \text{ mg/dL}$ ($\pm 0.67 \text{ mmol/L}$), $\pm 15 \text{ mg/dL}$, ($\pm 0.83 \text{ mmol/L}$), and $\pm 20 \text{ mg/dL}$ ($\pm 1.11 \text{ mmol/L}$)will be computed.

The *RD* and *D* distribution tables will be constructed using a threshold of 100 mg/dL (5.55 mmol/L).

As discussed in section 14.1 (Sample Size), with n = 240, the critical number (minimum) of accurate results is 228, which yields approximately 95% chance of satisfying the criterion if the actual probability that any result will be accurate is at least 96.77%. Symbolically, this criterion is equivalent to testing the hypothesis:

*H*₀ : *Prob{accurate}*<96.77% versus the alternative:

H_1 : Prob{accurate} $\geq 96.77\%$

This test has a power of about 95%, with n = 240, to reject H₀ if the actual probability of obtaining an accurate result is 96.77%. Conversely, there is about a 95% chance that the null will NOT be rejected if the actual probability that a result with the evaluation device would satisfy this definition of accuracy is only about 92.03%. It is possible that the sample size after the study is completed may not be exactly 240. The critical values will be approximately 95% or 98% of results (first and second parts of primary objective, respectively), and the associated hypotheses will be adjusted to reflect the change while maintaining no more than a 95% chance of rejecting the null hypotheses.

14.5.3 The second part of the primary objective states that at least 98% of the n = 240 results must fall within $\pm 15 \text{ mg/dL}(\pm 0.83 \text{ mmol/L})$ of the comparator result

(comparator < 75 mg/dL/4.16 mmol/L)) or $\pm 20\%$ of the comparator result (comparator ≥ 75 mg/dL/4.16 mmol/L). Thus, with n = 240, there must be at least 236 BGMS results satisfying this requirement. This is equivalent to testing the hypotheses:

*H*₀: *Prob{accurate}*<98.33% versus the alternative:

*H*₁: *Prob*{accurate } \geq 98.33%

There is approximately a 95% chance of rejecting H_0 in favor of H_1 if the actual probability that a meter measurement would satisfy the ±15mg/dL (±0.83 mmol/L) or 20% is 98.33%. Conversely, there is about a 95% chance that the null will NOT be rejected if the actual probability that a result with the evaluation device would satisfy this definition of accuracy is only about 96.23%.

14.6 Hematocrit Analysis – Other Objectives

- 14.6.1 Hematocrit will be measured for each participant. Mean, median, minimum, maximum, and standard deviation, will be computed for hematocrit determinations.
- 14.6.2 The effect of hematocrit on meter results will be presented via regression of differences between the meter and laboratory BG measurements against hematocrit.

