14.0 Statistical Plan

14.1 Sample Size

- 14.1.1 The sample size requirement is based on the primary objective, section 8.0.
- 14.1.2 There will be a minimum of N = 120 study samples entered into the study. The meter results will be taken in duplicate, so that the total sample size of meter results will be 2*120 = 240.
- 14.1.3 With a sample size of n = 240 results, there is approximately a 95% chance that at least 228 of those results (95% of 240) will be "accurate" (errors within either ±12 mg/dL (±0.67 mmol/L) when the comparator result is < 100 mg/dL (5.55 mmol/L), or ±12.5% when the comparator result is \ge 100 mg/dL (5.55 mmol/L) if the evaluation (meter) system has a 96.77% chance of yielding an "accurate" result.
- 14.1.4 Conversely, there is about a 95% chance of obtaining fewer than 228 "accurate" results if the system only has an approximately 92.03% chance of yielding an accurate result.

14.1.5 Note that each glucose result obtained with the evaluation devices will be considered either 'accurate' or 'not accurate, where accuracy depends on the particular test criterion as described in section 7.0 of this protocol.

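### The nulls written for the two primary accuracy criteria (below 96.77% and below 98.33%) are not controlled by the 228/240 and 236/240 rules, and the 95% chance of passing stated at 98.33% is really 63%

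*Combined protocol and SAP*

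**What the plan says.** Sections 8.1.1 and 8.1.2 set two criteria for each device: at least 95% of results within the tighter limits, and at least 98% within the wider ones. Section 14.1 plans 120 samples, each measured twice by each meter ("The meter results will be taken in duplicate"), giving n = 240 results.

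- **Criterion 1 (14.1.3, 14.1.4, 14.5.2).** The pass mark is 228. The stated chance of passing is about 95% at a true accuracy of 96.77%. The stated chance of failing is about 95% "if the system only has an approximately 92.03% chance of yielding an accurate result". Section 14.5.2 then adds "Symbolically, this criterion is equivalent to testing the hypothesis" H0: p < 96.77% against H1: p ≥ 96.77%, and calls the 95% at 96.77% the power.
- **Criterion 2 (14.5.3).** For n = 240, "there must be at least 236 BGMS results satisfying this requirement". The hypotheses are H0: p < 98.33% against H1: p ≥ 98.33%. "There is approximately a 95% chance of rejecting H_0 in favor of H_1" is stated for a true accuracy of 98.33%, and about a 95% chance of not rejecting at 96.23%.
- **Final n other than 240 (end of 14.5.2).** The critical values stay at about 95% and 98% of results, and "the associated hypotheses will be adjusted to reflect the change while maintaining no more than a 95% chance of rejecting the null hypotheses".

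**The concern.** A test is controlled when the chance of rejecting is small everywhere in the null, including at its boundary. In both criteria the plan places the null boundary at the accuracy where it also claims a 95% chance of rejecting. A device just inside the null would then be passed almost as often as one just inside the alternative. For criterion 2 the boundary also equals the observed proportion at the pass mark, so a 95% chance of passing there is implausible on its face.

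These are the only inferential statements made for the primary objective. Rejecting H0 as written means concluding that accuracy is at least 96.77% or at least 98.33%, which a bare pass does not show. The sponsor's own risk of failing criterion 2 is understated as well. For any final n other than 240, the limit offered is a 95% ceiling on rejecting the null, which does not limit false passes.

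**Working it through.** **Inputs.** n = 240, pass marks 228 and 236, and accuracies 96.77%, 92.03%, 98.33% and 96.23%, all from 14.1 and 14.5. Results are treated as independent, which is the assumption under which the plan's own criterion 1 figures reproduce.

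**Formula.** The chance of passing at true accuracy p with pass mark r is P(X ≥ r), where X ~ Binomial(240, p). The size of a written test is the largest chance of passing over its null, which is reached at the boundary.

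**Step 1. The plan's figures.**

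| Rule | True p | Plan's chance of passing | Exact |
|---|---|---|---|
| ≥ 228 | 96.77% | about 95% | 0.950 |
| ≥ 228 | 92.03% | about 5% | 0.050 |
| ≥ 236 | 98.33% | about 95% | **0.627** |
| ≥ 236 | 96.23% | about 5% | 0.050 |

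Three figures reproduce and one does not. Approximations do not rescue it: normal 0.498, normal with continuity correction 0.598, Poisson 0.627.

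**Step 2. Where 98.33% comes from.** 236/240 = 0.9833, so it is the pass mark as a proportion. Solving P(X ≥ 236) = 0.95 gives p of about 99.18% (check: 0.951 at 99.18%). A 95% chance of passing at 98.33% would fit a pass mark of 233 (0.950), but 233/240 = 97.1% breaks the 98% criterion. At 98.33% the chance of failing is 1 − 0.627 = 37%, not 5%.

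**Step 3. Size of the tests as written.** At the boundaries, criterion 1 has size 0.950 and criterion 2 has size 0.627. Testing these nulls at one-sided 5% would need far higher pass marks:
- p < 96.77%: 237/240 (0.047; 236 gives 0.111).
- p < 98.33%: 240/240 (0.018; 239 gives 0.089).

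**Step 4. What the rules do control.** Size is 0.050 at 92.03% for the 228 rule and 0.050 at 96.23% for the 236 rule. Exact one-sided 95% lower bounds agree: 228/240 gives 92.0% and 236/240 gives 96.2%. Between the two points, the 228 rule passes 58% of the time at 95% and 83% at 96%. The 236 rule passes 47% of the time at 98%.

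**Step 5. Final n other than 240.** Up to 150 participants (9.2) allows 2 × 150 = 300 results. With the pass mark rounded up to an integer:

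| n | Pass marks | Criterion 1 size at 92.03% | Criterion 2 size at 96.23% |
|---|---|---|---|
| 250 | 238, 245 | 3.5% | 8.8% |
| 260 | 247, 255 | 4.3% | 7.1% |
| 280 | 266, 275 | 3.6% | 4.6% |
| 300 | 285, 294 | 3.0% | 6.3% |

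Only even n arise, because 14.7.6 excludes a sample with a missing replicate. Criterion 2 size is above 5% at every even n from 250 to 276 (5.01% at 276, against 5.02% at 240) and again at 300.

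**Step 6. Sensitivity to duplicates.** The documents give no within-sample correlation, so this is an assumed range. Take 120 pairs with P(both accurate) = p² + ρp(1 − p). At ρ = 0.25, 0.5 and 1, size is 7.1%, 9.2% and 14.9% for criterion 1, and 7.2%, 9.4% and 16.6% for criterion 2. At ρ = 1 the lower bounds become those for 114/120 and 118/120, which are 90.4% and 94.8%.

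**The case against.** The strongest reply is that nothing depends on the hypotheses. A device passes on its observed share of results, at least 95% and at least 98%, under criteria the plan takes from CLSI, and no choice of H0 changes which counts pass. For criterion 1 the operating characteristics are correct and already disclosed as a two-point design, with 96.77% and 92.03% as the accuracies for a likely pass and a likely fail. Since 96.77% lies in H1, calling the 95% there power is literally true. For other n the plan does fix the critical proportions, and criterion 1 stays below 5% at the sizes tabulated. Nowhere does the plan say that a pass will be reported as p ≥ 96.77% or p ≥ 98.33%. Finally, 92.03% and 96.23% are back-calculated from the pass marks and have no clinical justification in the documents.

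Most of this is fair, and it limits the consequence: the pass rule stands, and criterion 1 is a misplaced null rather than a wrong probability. It does not remove the fault. The plan chose to present the rules as tests, the written alternatives are what rejection would assert, one stated probability is wrong by 32 percentage points (95 − 63), and the 95% cap is not error control. The duplicate correlations are assumed and the point does not depend on them.

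**Conclusion.** The concern holds. As written, the two tests have sizes of about 95% and 63%, and the stated 95% chance of passing criterion 2 at 98.33% is 63%. The rules themselves are tests of p ≤ 92.03% and p ≤ 96.23% at about 5%, with about 95% power at 96.77% and 99.18% respectively. These figures assume 240 independent results. Positive correlation between duplicates would raise the false-pass rates above 5% and lower what a pass supports. What is affected is the inferential claim, the stated risk of failing criterion 2, and error control when n is not 240. Which counts pass at n = 240 is not affected.

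**What to change.** 1. Restate criterion 1 as H0: p ≤ 92.03% against H1: p > 92.03% (size about 5%, power about 95% at 96.77%). Restate criterion 2 as H0: p ≤ 96.23% against H1: p > 96.23% (size about 5%, power about 95% at 99.18% and about 63% at 98.33%). Correct the 95% now stated at 98.33%. Dropping the hypotheses and giving the pass rules with correct operating characteristics would also remove the contradiction.
2. Fix the nulls before the data are seen. For any final n, set the pass marks at the smallest integers not below 0.95n and 0.98n, in line with 8.1.
3. Delete the 95% cap and state the actual size at the final n, noting that for criterion 2 it can exceed 5% (8.8% at n = 250).
4. Report a one-sided 95% lower bound per criterion and device. Either say that the exact binomial bound assumes independent duplicates, or use a bound that allows for clustering by sample.
5. Word a pass as having met the CLSI criterion. Claim p ≥ 96.77% or p ≥ 98.33% only if the lower bound supports it.

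The cost is SAP wording, one corrected figure and four lower bounds (two criteria × two devices). Sample size and the pass marks at n = 240 stay as they are. The downside for the sponsor is a less favourable stated claim.

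### Section 14.5.3 claims about 95% power for the 98% criterion at a true accuracy of 98.33%; under the plan's own rule and model it is 62.7%

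*Combined protocol and SAP*

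**What the plan says.** Section 8.1 lists two accuracy criteria under the primary objective. Criterion 1 (8.1.1) requires at least 95% of results within ±12.5% or ±12 mg/dL of the reference. Criterion 2 (8.1.2) requires at least 98% within ±20% or ±15 mg/dL.

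Section 14.1.2 fixes the number of results for each system: 120 samples are tested in duplicate, "so that the total sample size of meter results will be 2*120 = 240".

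For criterion 1, sections 14.1 and 14.5.2 say "the critical number (minimum) of accurate results is 228". They give a 95% chance of passing at a true accuracy of 96.77% and a 95% chance of failing at 92.03%.

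For criterion 2, section 14.5.3 says that "at least 98% of the n = 240 results must fall within" the limits, and continues: "Thus, with n = 240, there must be at least 236 BGMS results satisfying this requirement". It places the boundary between the null and alternative hypotheses at 98.33%. It then states, for a true accuracy of 98.33%, "There is approximately a 95% chance of rejecting H_0 in favor of H_1". Finally it gives about a 95% chance of not rejecting the null at a true accuracy of about 96.23%.

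**The concern.** The pass mark as a proportion is 236/240 = 98.33%. A system whose true accuracy equals the pass mark expects to land on the mark, so it should pass somewhat more than half the time, not 95% of the time. Criterion 1 is built differently. Its pass mark is 228/240 = 95%, and the 96.77% quoted for 95% power lies clearly above it. This suggests that the pass-mark proportion was entered in 14.5.3 where the design accuracy belonged.

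The error concerns the stated power of a primary criterion. Section 14.1 says the sample size is based on the primary objective but works through criterion 1 only, so 14.5.3 is the only place where the chance of meeting criterion 2 is stated. A reader would conclude that a system with 98.33% accuracy nearly always passes. Section 14.5.2 also says the hypotheses will be adjusted if the final number of results is not 240, and whoever carries the 98.33%/95% pairing forward would repeat the error.

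**Working it through.** **Inputs.** n = 240 results per system (14.1.2). Pass mark for criterion 1: 228 (14.5.2). Pass mark for criterion 2: 0.98 × 240 = 235.2, rounded up to 236 (14.5.3).

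**Formula.** With results treated as independent, as the plan's figures imply, the number accurate is X ~ Binomial(240, p), and the chance of passing is P(X ≥ r | p) for pass mark r.

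**Step 1: reproduce the plan's other figures.**

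| Quantity | Plan | Exact binomial |
|---|---|---|
| P(X ≥ 228), p = 0.9677 | about 95% | 0.9503 |
| P(X < 228), p = 0.9203 | about 95% | 0.9497 |
| P(X < 236), p = 0.9623 | about 95% | 0.9498 |

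All three agree, so the model is the one the plan used.

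**Step 2: the disputed figure.** Passing means at most 240 − 236 = 4 inaccurate results. At p = 0.9833 the expected number of inaccurate results is 240 × 0.0167 = 4.008, almost exactly the number allowed. The probabilities of 0, 1, 2, 3 and 4 inaccurate results are:

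0.0176 + 0.0716 + 0.1453 + 0.1958 + 0.1970 = 0.627

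The plan says about 0.95. The gap is 95 − 62.7 = 32.3 percentage points. At a true accuracy of exactly 98%, the chance of passing is 0.475.

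**Step 3: the accuracy that does give 95%.** Solving P(X ≥ 236 | p) = 0.95 gives p = 0.99176, or 99.18%. As a check, P(X ≥ 236 | 0.9918) = 0.951.

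**Step 4: can another reading recover 95% at 98.33%?**

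| Variant at p = 98.33% | Chance of passing |
|---|---|
| p = 236/240 unrounded | 0.629 |
| Poisson approximation | 0.627 |
| Normal approximation, without / with continuity correction | 0.498 / 0.598 |
| Pass mark 235 | 0.785 |
| Pass mark 234 | 0.890 |
| Pass mark 233 | 0.950 |
| Correlation within duplicates from 0 to 1 | 0.62 to 0.68 |
| 150 participants: 300 results, pass mark 294 | 0.762 |

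Only a pass mark of 233 gives 95%, and 233/240 = 97.1% breaks the 98% rule.

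**The case against.** The strongest counter-argument accepts the arithmetic and disputes the consequences.

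- **The decision rule does not change.** The 98% requirement and the mark of 236 are stated independently of the power sentence, and no result would be reclassified. The worked sample-size argument in 14.1 rests on criterion 1, so n = 240 is not shown to depend on the wrong figure. This stands.
- **Criterion 2 need not be the one that limits success.** Its limits are wider than those of criterion 1 at every glucose level, so which criterion binds depends on the error distribution. As an illustration, assume unbiased normal relative errors and all references at or above 100 mg/dL. A system at 96.77% on criterion 1 then has an error SD of 5.84%, is 99.94% accurate on criterion 2, and passes criterion 2 with probability above 0.999. A system at 98.33% on criterion 2 would be only about 86.5% accurate on criterion 1 and would almost never pass that. This also stands: 62.7% is the correct value at the accuracy the plan chose, not a forecast of the study's overall power.
- **A joint figure for the two systems is only illustrative.** If they were independent, both would pass criterion 2 at 98.33% with probability 0.627 × 0.627 = 0.39. However, they are tested on the same samples against the same reference, and the plan states no rule that both must pass. The finding does not depend on this number.

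None of these points supports 95% at 98.33%.

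**Conclusion.** The concern holds. At a true accuracy of 98.33%, the chance of meeting the rule of at least 236 of 240 is 62.7%, not about 95%. A 95% chance needs a true accuracy of 99.18%. Of the four operating figures given for the two criteria, this is the only one that does not reproduce, and it overstates the chance of passing a primary criterion.

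The calculation assumes 240 independent results, as the plan does. Correlation within duplicates leaves the figure at 98.33% between 0.62 and 0.68. It would, however, lower the pass chance at 99.18% from 0.951 to between about 0.91 and 0.93 for correlations of 0.25 to 1. The 99.18% should therefore be labelled as resting on independence.

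**What to change.** Correct the power sentence in section 14.5.3 in one of two ways:

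- give 99.18% as the true accuracy at which there is about a 95% chance of at least 236 of 240; or
- keep 98.33% and give the chance as about 63%.

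Leave the pass mark of 236 and the 96.23% figure as they are. Add the same operating characteristics for criterion 2 to section 14.1, and state that they assume independent results.

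Confine the edit to the power sentence. The value 98.33% also appears in the hypotheses of 14.5.3; where that boundary should lie is a separate question, and a blanket replacement by 99.18% would not settle it.

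The cost is a wording change in the combined protocol and SAP. No extra samples are needed and the decision rule does not change, but the stated operating characteristic becomes less favourable.

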8.0 Objectives and Hypotheses

The primary objective of the study is to evaluate the performance of Contour Next and Contour Plus Elite BGMSs with residual arterial blood samples. The performance of the BGMS will be analyzed according to the following objectives:

- 8.1 Primary Objective: The accuracy criteria below are taken from the CLSI. *Point-of-Care Blood Glucose Testing in Acute and Chronic Care Facilities; Approved Guideline – Third Edition.* CLSI document POCT12-A3. Wayne, PA: Clinical and Laboratory Standards Institute; 2013).
 - 8.1.1 At least 95% of all blood glucose results shall fall within ±12.5% of reference values (laboratory method) for glucose concentration ≥100 mg/dL (5.55 mmol/L) and within ±12 mg/dL (±0.67 mmol/L) at glucose concentrations <100 mg/dL (5.55 mmol/L).

Note: Satisfying Criterion 8.1.1 would also satisfy the ISO 15917:2013 criteria of obtaining the $\pm 15\%$ of reference values (laboratory method) for glucose

concentration $\geq 100 \text{ mg/dL} (5.55 \text{ mmol/L})$ and within $\pm 15 \text{ mg/dL} (\pm 0.83 \text{ mmol/L})$ at glucose concentrations < 100 mg/dL (5.55 mmol/L).

8.1.2 At least 98% of values shall be within ±20% of reference values (laboratory method) for glucose concentration ≥75 mg/dL (4.16 mmol/L) and within ±15 mg/dL (±0.83 mmol/L) at glucose concentrations < 75 mg/dL (4.16 mmol/L).

8.2 Other Objectives:

Compute differences between BGMS and laboratory blood glucose measurements and plot them against hematocrit results.

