12.0 Procedures

12.1 Summary

Laboratory professionals will test the blood glucose concentration of residual arterial blood samples, collected (into a tube with anticoagulant) from participants using the Contour Next and Contour Plus Elite BGMSs. For participant's safety reasons, only residual arterial blood will be used which had been collected as prescribed for clinical testing and is no longer needed for clinical purposes.

A minimum of 120 residual arterial blood samples will be tested with both BGMSs in duplicate. Approximately 2mL of whole blood will be removed from the participant's sample tube and will be used for completing a total of 4 tests using both BGMSs (two tests with Contour Next BGMS and two tests with Contour Plus Elite BGMS), a hematocrit measurement, and duplicate laboratory glucose measurements. Each participant sample will be tested using both BGMS as per the randomization schedule. After completion of the BGMS testing, each meter will be cleaned and disinfected as per the procedures in Appendix A.

The site staff will use their Laboratory Analyzer (approved by the Sponsor) for the laboratory assessment of blood glucose samples tested in duplicate (laboratory duplicate results will be averaged).

During the study, a minimum of 10 test strip vials (50 test strips in each vial) that cover a minimum of 3 test strip lots will be used for each BGMS. The test strip lots will be randomly coded as green, blue, or red to easily identify the bottles during the study. See Table 1 for the description of test strip distribution during the study (note: the 3 test strip lots are arbitrarily designated as Red, Green, or Blue).

Blood samples will be assigned to one of three test strip lots. The assignment will be made in a rotating order following the random order in which samples are received.

The order of testing for both BGMSs will also be randomized for each sample.

Meter System & Test Strips	Green Lot	Red Lot	Blue Lot	
	~40 Samples ~80 tests	· ^	~40 Samples ~80 tests	
	~40 Samples ~80 tests	^	~40 Samples ~80 tests	

 Table 1 - Strip Lot Assignments Per Meter Type

12.2 Study Staff Training

The site study staff will participate in a training session conducted by the Ascensia Study team or designee. The training will be documented and the following will be reviewed:

- 12.2.1 Protocol & case report forms
- 12.2.2 Review of the instructions for use (UG)
- 12.2.3 Review of meter control solution testing

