14.4 Weighted Least Squares Regression

Weighted least squares regressions of meter results against comparator results will be performed. If M represents the meter result, and C the comparator result, the linear model can be expressed as:

$$M = \beta_0 + \beta_1 C + \varepsilon$$
$$\varepsilon \sim N(0, cv * C)$$

The parameter cv is the coefficient of variation, which is assumed to be constant across the glucose range. The weighting function will be:

$$w = C^{-2}$$

This weighting function is used to account for the constant cv nature of glucose measurement (Draper and Smith, 1998).¹

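### Does the hematocrit regression in 14.6.2 need a stated difference scale, weights and a rule for the duplicate meter results?

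*Combined protocol and SAP*

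**What the plan says.** The hematocrit work is listed under other objectives. Section 8.2 asks the analyst to "Compute differences between BGMS and laboratory blood glucose measurements and plot them against hematocrit results". Section 14.6.1 adds summary statistics for hematocrit, and 14.6.2 adds that "The effect of hematocrit on meter results will be presented via regression of differences between the meter and laboratory BG measurements against hematocrit".

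Four other places bear on how that regression would be run:

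- Section 14.4, for the regression of meter on comparator, sets the error SD to cv times C. It says "The parameter cv is the coefficient of variation, which is assumed to be constant across the glucose range", and of the C^-2 weights, "This weighting function is used to account for the constant cv nature of glucose measurement".
- Section 14.5.1 defines RD, a percent difference, at or above the glucose threshold. Below it, the plan has "Difference (D) for reference result < threshold glucose", which is M - C.
- Section 14.3 uses the unqualified word difference for each device result minus the reference result.
- Section 12.1 states that "laboratory duplicate results will be averaged". Section 14.1.2 takes the meter results in duplicate, "so that the total sample size of meter results will be 2*120 = 240". Hematocrit is measured once per participant, and 14.7.6 makes a sample non-evaluable if a meter replicate is missing.

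**The concern.** Three choices are left open in 14.6.2: the scale, the weights and the treatment of duplicates. Two analysts could follow the section faithfully and report slopes in different units, mg/dL or percent per hematocrit point.

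The plain reading is an unweighted regression of M - C over the whole glucose range. If error SD is proportional to glucose, as 14.4 assumes, high-glucose samples dominate the error of that slope. The plan would then be using one error model in 14.4 and ignoring it in 14.6.

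The two meter results for a sample share one hematocrit value and one averaged reference, so their errors are correlated. Section 14.1 counts them as 240 results. If the regression did the same and an interval were reported, that interval would be too narrow and a hematocrit effect could be read into noise. This is the plan's only analysis of hematocrit, in a population where Section 5.0 itself warns that meter performance may differ.

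**Working it through.** **1. The plan's own figure.** Section 14.1.3 gives about a 95% chance of at least 228 accurate results of 240 if "the evaluation (meter) system has a 96.77% chance of yielding" an accurate result. The exact binomial P(X >= 228 | n = 240, p = 0.9677) is 0.950, so the figure reproduces and treats the 240 results as independent. With no bias and normal relative error, 96.77% within 12.5% implies a relative SD of 12.5 / 2.14 = 5.84%. The documents give no figure for the hematocrit regression.

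**2. Scale.** Assumptions not in the documents: glucose C is lognormal with log-SD s from 0.2 to 0.5 and independent of hematocrit; the hematocrit effect is proportional to glucose; error SD is proportional to C^p. Expressed as a fraction of the effect, the standard error of the M - C slope over that of the RD slope is

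sqrt(E[C^(2p)]) / (E[C] × sqrt(E[C^(2p-2)])) = exp(s²(2p - 1.5)).

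| p | s = 0.2 | 0.3 | 0.4 | 0.5 |
|---|---|---|---|---|
| 1 (Section 14.4) | 1.020 | 1.046 | 1.083 | 1.133 |
| 0.69 | 0.995 | 0.989 | 0.981 | 0.970 |

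The two scales are equal at 2p = 1.5, that is p = 0.75. At p = 1, M - C loses 2% to 13%. At p = 0.69 it is ahead by 0.5% to 3%.

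**3. What the documents say about p.** The precision tables in the attached user guides allow log-log fits of SD on concentration:

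- Contour Next repeatability in whole blood: SD 0.06, 0.07, 0.11, 0.18, 0.24 at 2.23, 4.36, 7.63, 11.80, 18.94 mmol/L gives p = 0.69. The lowest row is garbled (its SD lies outside its printed interval); without it p = 0.86.
- Contour Next control solution: SD 0.03, 0.10, 0.38 at 2.34, 6.39, 20.55 gives p = 1.17, or 1.11 from the printed CVs.
- Contour Plus Elite control solution, from the printed CVs of 1.3%, 1.1%, 1.2% at 2.58, 7.09, 20.77: p = 0.96.

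The only whole-blood table moves across the 0.75 break-even when one damaged row is dropped. All three tables show precision, not total error against a laboratory method. They do not settle which scale is more precise.

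**4. Bias.** Simulated studies of 120 samples (6,000 runs) had one averaged row per sample, glucose median 150 mg/dL, an assumed glucose-hematocrit correlation of 0.3 and no hematocrit effect. The share of 95% intervals that excluded zero, over s = 0.2 to 0.5, was:

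| Assumed meter bias | M - C | RD |
|---|---|---|
| 5 mg/dL constant | 5% to 6% | 7% to 18% |
| 4% proportional | 7% to 17% | 4% to 6% |

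Each scale is protected against one kind of bias and exposed to the other. The 4% row is illustrative only: with SD 5.84% that system would be 92.5% accurate, below the 96.77% planning value. Adding 1/C to the RD model brings the constant-bias figure back to about 5%, but its power can then fall below that of M - C (78% to 79% against 83% to 84% at p = 0.69, for an assumed effect of 0.25% per hematocrit point).

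**5. Duplicates.** Every evaluable sample has exactly two meter results at the same hematocrit value, so unweighted least squares on 240 rows and on 120 sample means gives the same slope. Only the standard error differs. With within-sample error correlation rho, an interval from 240 rows taken as independent has relative width 1/sqrt(1 + rho), and excludes zero under no effect with probability 2(1 - Φ(1.96/sqrt(1 + rho))):

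| rho | Relative width | False exclusion of zero |
|---|---|---|
| 0.5 | 0.816 | 11% |
| 0.8 | 0.745 | 14% |
| 0.95 | 0.716 | 16% |

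A rho in this range is plausible. If within-pair noise is the Contour Next repeatability CV of 1.3% to 2.8%, the shared part of the variance is 1 - (1.3/5.84)² = 0.95 down to 1 - (2.8/5.84)² = 0.77. At an assumed total SD of 4% it is 0.89 down to 0.51. The error is real, but it arises only if an interval is reported and the pairing is ignored.

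**The case for a change.** The strongest case for a change is that the omissions are genuine, that one or two sentences would close them, and that settling the scale beforehand removes a post hoc choice. The duplicate gap does not depend on the assumed glucose spread: any positive correlation within pairs makes a 240-row standard error too small. The precision loss can also exceed 13%. If the hematocrit effect is constant in mg/dL and error follows 14.4, C^-2 weighting beats unweighted M - C by exp(2s²), or 8% to 65% over the same range of s.

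The omissions stand, and so does the direction of the duplicate effect. The rest is weaker. The scale is less open than it looks: 14.5.1 calls M - C the difference and gives the other metric a qualified name, and 14.3 uses the bare word for meter minus reference. The 65% needs the widest assumed glucose spread, a constant effect and exactly proportional error together; at p = 0.69 the same comparison gives 3% to 21%. Because M - C and RD slopes estimate different quantities, a precision ratio has meaning only once the form of the effect is assumed. The duplicate problem requires an interval that the plan does not call for. Section 14.2 also refers the analysis to a CLSI guideline that was not available here and may fix the presentation.

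**Conclusion.** No change to the plan follows. Section 14.6.2 is short on detail, but for an analysis that the plan only computes, plots and presents. No conclusion about either meter rests on its standard error, and both primary accuracy criteria are untouched.

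On scale and weights this is a fair trade-off. Against M - C, RD gains 2% to 13% in precision under the 14.4 model with a proportional effect. It loses 0.5% to 3% at the exponent of the whole-blood table, and it does worse under constant meter bias. These figures rest on an assumed lognormal glucose distribution, form of effect and glucose-hematocrit correlation that the documents do not give.

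On duplicates the gap is one that analysts fill sensibly. The point estimate is the same either way. Anyone who adds an interval can see that two results share one hematocrit value and one reference, and would average them or cluster by sample. Labelling the units of the slope in the report settles the rest.
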